7.2 Secondary Efficacy Endpoints

Secondary efficacy endpoints in this study will include:

- Re-epithelialization to a Category 1 or lower. The patient may still have erythema at the site. Pain scores during incontinence management will be measured on a 0-10 Faces Pain Scale Visual Analog and will be analyzed only for those adult subjects who can report pain. Pain scores during incontinence management will be measured on the FLACC scale for pediatric patients.
- Efficacy in subjects who switch from the comparative product to Cavilon Advanced Skin Protectant after failure to completely heal on the comparative product.
- Prevention of IAD, as measured by either:
- Areas of the buttocks that were free of IAD and remained free of IAD throughout the intervention
- IAD scores in subjects whose IAD improved and who continued on Cavilon Advanced Skin Protectantt.
- $\circ~$ The proportion of subjects who have no progression of IAD, while still experiencing incontinence, will be estimated.
 - Patient Quality of Life (QoL) as measured by the EQ-5D-5L questionnaire will be analyzed by comparing the change from baseline in each of the domains. The changes from baseline will be compared using an analysis of variance with center, product, type of skin (denuded or not), and interactions as factors in the model.
 - Nursing time will be summarized for time and motion to be completed on 2 subjects at each participating study site (one patient in each arm of the study). Each subject will have time and motion measured during a fecal incontinence episode
 - Incontinence product use will be recorded during the study, and summarized for both product groups. Product utilization, such as estimated cost per application, frequency of application and days of treatment will be considered. The purpose of this analysis is to provide estimates of total IAD management cost for both regimens.
 - Prevention of complications such as fungal infections and or pressure ulcer development.
 - Environmental cleanliness of multi-use comparative product packaging.

7.3 Safety Endpoints

Assessment of the safety of Cavilon Advanced Skin Protectant compared to the comparative product will be based upon analyses of the number and percent of subjects with an adverse event (AE) and the nature of each AE. The data will be summarized for each group based on the number and percent of subjects reporting AEs and will be summarized by product group and overall. In addition, AEs will be categorized and then summarized by relation to product and severity/intensity. Incidence of discontinuation will be summarized by reason for discontinuation for each product group.

8. Study Population

The study population will consist of subjects suffering from severe Category 2 Incontinence-Associated Dermatitis where the epidermis has been breached, or the skin is denuded, and who are

in a facility that provides nursing care 24 hours a day. Subjects' incontinence may be urinary and/or fecal, and can be continuous or non-continuous during the 21-day follow-up period. The subjects should not have any pre-existing fungal infections or stage 3, or stage 4 pressure ulcer(s) in the sacrococcygeal and buttock area. Subjects with Stage 1 or Stage 2 pressure ulcers maybe enrolled. (Note, no dressings are allowed for Stage I/II pressure ulcers.) Subjects with ostomies may be enrolled if the anal opening is present and there is evidence of denudement in the perianal or surrounding areas. Also subjects with fecal management systems may be enrolled if there is evidence of denudement in the perianal or surrounding areas. Subjects enrolled must meet the Inclusion/Exclusion criteria set forth in Section 8.1 and 8.2.

8.1 Subject Inclusion Criteria

Subjects may be enrolled into this study if the answers to all these questions are yes.

- 1. Is the subject a full-term newborn (37 weeks or greater gestational age) or older?
- 2. Is the subject in a facility providing nursing care 24 hours per day?
- 3. Does the subject have severe Category 2 Incontinence-Associated Dermatitis –red with skin breakdown (i.e. skin erosion and denudation or denudation of skin alone)?
- 4. Is the subject willing to have photos taken of their skin exposed to incontinence and permit use of photographs in potential publication?
- 5. Is the subject willing to release rights to 3M for the use of the photos?
- 6. Is there a reasonable expectation that the subject will remain in a facility for at least 7 days following enrollment in the study?
- 7. Has the subject, or their legally authorized representative, signed an Institutional Review Boardapproved informed consent/assent document and authorized the use and disclosure of protected health information?

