6.3 Sample Size

102 eligible subjects will be enrolled in this study across approximately 13 centers, with 51 subjects being enrolled in each product group. it is expected that each center will enroll between 8 and 15 subjects. If it is determined that ineligible subjects were enrolled (e.g. without denudement at baseline or leaving the study prior to the first assessment day), additional subjects will be enrolled so that a total of 102 eligible subjects will be enrolled in the study.

Page 16 of 54 Status: Release Version: 7 Issue Date: 8/31/2016 12:19:02 PM

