9.4 Confidentiality of Data

The Principal Investigator will oversee the conduct of the study and all data will be kept confidential. Confidentiality will be maintained by using patient identification numbers instead of names. Consent forms, data collection sheets and records, linking a subject's name with their ID number will be maintained in a locked cabinet or locked office. Information to be stored on the computer will be identified by subject ID and will be password protected. Data disclosed outside the study team will be de-identified or will only include general group demographic information. Protected Health Information and/or identifiable study data will not be shared with anyone outside the study team or Health System, with the exception of the study sponsor, and federal regulators/ institutional officials for the purposes of auditing.

10. Screening and Enrollment

Subjects enrolled Week 1 will follow the following application/assessment schedule: M-W-F, T-TH-SAT, W-F or Th-Sat.

Week 2 and Week 3 application/assessment schedule will always follow M-W-F schedule. Subjects enrolling later in the week will need to be followed up by study coordinators for application 9 (M) in Week 4.

A representative from the site will complete the following screening and enrollment activities:

- Obtain Informed Consent
 - Explain the study to the subject, answer questions, and obtain written informed consent
- Review the Inclusion/Exclusion Criteria.
- Perform assessments required by the Inclusion/Exclusion criteria.
 - Collect urine sample and perform urine pregnancy test for female subjects who are of childbearing age. If the subject is post-menopausal, no pregnancy test is required.

3M is using the IAD Severity Categorisation Tool from Beeckman D et al Proceedings of the Global IAD Expert Panel (2015) for current classification of IAD. Attached below is Table 1, IAD Severity Categorisation Tool displaying the severity of IAD and associated signs for the study investigators use in categorizing subjects. Only subjects with a Category 2 level of IAD will be enrolled into this study.

TABLE 1 | IAD Severity Categorisation Tool

Clinical presentation	Severity of IAD	Signs**
	No redness and skin intact (at risk)	Skin is normal as compared to rest of body (no signs of IAD)
	Category 1 - Red* but skin intact (mild)	Erythema +/-oedema

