	Category 2 - Red* with skin breakdown (moderate-severe)	As above for Category 1 +/-vesicles/bullae/skin erosion +/- denudation of skin +/- skin infection

If a subject does not meet all the Inclusion/Exclusion criteria, and is excluded from the study, the reason(s) for exclusion will be documented on the Screening Log.

If a subject meets all the Inclusion/Exclusion criteria, the Investigator or study nurse will obtain and open the randomization envelope to determine which product group the subject has been assigned to. The study nurse will complete the following remaining screening activities:

- Record subject demographics.
- Obtain and record IAD history.
- Obtain and record information describing current medications and IAD treatment.
 - Oral or systemic medications prescribed by the subject's physician are allowed and will be noted on the appropriate CRF.

- Incontinence-related devices (such as urinary catheters, pads, diapers, etc.) are allowed and will be noted on the appropriate CRF.
- Use of moisture barrier, creams, ointments, pastes, or other topical medications in combination with the Cavilon Advanced Skin Protectant product for the management of IAD is **not** allowed.
- If subjects had prior barrier film products on their skin, use the Brava Adhesive Remover Wipe.
- Conduct pressure ulcer risk assessment using Braden Scale.
- Administer Quality of Life questionnaire.
- Perform skin cleansing:
 - Use 3M[™] Cavilon[™] No-Rinse Skin Cleanser (to be provided by 3M) or warm tap water and soft cloths.
 - Avoid rigorous scrubbing to minimize friction damage.
 - Record pain score assessment using Faces Pain Scale Visual Analog before and after cleansing for adults or the FLACC scale for pediatrics during the cleansing process.
- Conduct skin assessment:
 - Complete a skin assessment of the following six zones for its color, presence of lesions, and skin loss. Only subjects with denuded skin may be enrolled. The IAD score will be calculated electronically once results are entered into computer system using 3M's validated Skin Condition Assessment Tool (see Appendix A).
 - Zone 1: Includes the anus and 2 inches surrounding anal opening plus: for males score the scrotal sac and females the labia majora.
 - Zone 2: Crease between buttocks, above the anal opening and 2-3 inches below natural waistline
 - Zone 3: Left buttock starts above fold between thigh and buttock and extends upward to 2-3 inches below natural waistline

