 - At each incontinence care episode, cleanse the skin with 3M[™] Cavilon[™] No-Rinse Skin Cleanser or warm tap warm with soft cloths. Gently dry. Avoid rigorous scrubbing to minimize friction damage.
 - Do not reapply Cavilon Advanced Skin Protectant between each incontinence cleansing episode. Follow the dosing schedule of either:
 - M-W-F, T-TH-Sat, W-F or TH-Sat for week 1. Week 2 &3 follow M-W-F.
 - For the comparative arm product must be applied at every incontinence cleansing episode.
- Healthcare Worker Ease of Use Survey (only after first dosing)
 - Complete product Ease of Use survey following application of Cavilon Advanced Skin Protectant
- Cavilon Advanced Skin Protectant Product Application
 - Following cleansing, the 3M[™] Cavilon[™] Advanced Skin Protectant will be applied 3 times a week following the M-W-F dosing schedule.
 - A thin coat of the Cavilon Advanced Skin Protectant will be painted on or dabbed onto the area covering the entire 6 zones. The Cavilon Advanced Skin Protectant product contains 2.4 mL of material which can cover a maximum area of 25 cm X 25 cm or 10 inches X 10 inches.

- More than one applicator may be necessary depending on the surface area involved. In the event that the contents of one applicator are not sufficient to cover the area requiring protection, additional applicators can be used as needed. Record the number of applicators used.
 - For subjects with IAD in the perineal area (front of body), the same product (either Cavilon Advanced Skin Protectant or comparative product) should be applied in the perineal area. This area will not be graded for IAD, but application of product in this area will be noted on the case report forms and the number of applicators used for the perineal area will be tracked separately from the applicators used on the buttocks.
- If there should be a need for product removal, use adhesive remover and gently wipe the area.
- Document the amount of product required to cover the entire affected area
- Record pain score using Faces Pain Scale Visual Analog before and after product application
- Clean Trace ATP System Evaluation after Sensi-Care Product Application
 - After all photos, patient assessments and after product application are completed, the Sensi-Care tube of paste used will be swabbed for environmental contamination using 3M Clean Trace ATP System.

• ConvaTec Sensi-Care® Protective Barrier Paste Application

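### Inclusion 3 requires denudation but not in a graded zone, so a subject can be randomized with a zero or very low baseline for the primary percent change

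*Combined protocol and SAP*

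**What the plan says.** **Eligibility.** Inclusion 3 (Section 8.1 and synopsis) requires severe Category 2 IAD with "skin erosion and denudation or denudation of skin alone". Both alternatives need denudation, and neither says where. Section 8 gives a location (perianal or surrounding areas) only for subjects with ostomies or fecal management systems.

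**Score.** Section 10 defines six zones whose scores are combined into one IAD score. Appendix A weights epidermal loss by 30 and abnormal colour of intact skin by 1, each multiplied by an area grade of 1 to 4. For IAD on the front of the body, Section 11.1 says: "This area will not be graded for IAD, but application of product in this area will be noted on the case report forms".

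**Order of screening.** In Section 10 the envelope is opened once the criteria are met. The six-zone assessment follows among the remaining activities, and that later bullet carries the line "Only subjects with denuded skin may be enrolled". The score is calculated electronically after data entry.

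**Analysis.** Section 19.1.1 compares percent change from baseline to last visit by analysis of variance, with ranking as an option. The document gives no minimum baseline score and no rule for a baseline of 0. Section 19.1.1 leaves detail to an approved SAP.

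**The concern.** A percent change needs a baseline well away from zero. The tool gives one whenever there is open skin in a graded zone, but the entry criterion is not tied to the graded zones. A subject denuded only in the ungraded front area meets inclusion 3 as written and contributes no epidermal-loss points at baseline.

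If the six zones look normal, the primary endpoint cannot be computed for that subject. If they show only some redness, one small new erosion in a graded zone produces a change of several hundred percent or more, and a single subject can dominate an arm mean. Because the zones are scored after allocation is known, in a study where the nurse applying the product is not blinded (Section 6.2), any decision about such a subject would be made with the arm known and without a written rule.

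**Working it through.** **Inputs.** 51 per arm, SD 70 and difference 45 (Section 19.2). Two-sided test, final significance level 0.0483 (Sections 19.2 and 19.3). Weights 30 and 1, area grades 1 to 4 (Appendix A), six zones (Section 10). Assumption: zone scores are summed, since Section 10 says only that they are combined.

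**1. The plan's own figure.** Power = Φ(45/70 × √(51/2) − 1.96) = Φ(3.246 − 1.960) = 90.1% at 0.05, and 89.8% at 0.0483. The stated power of at least 80% is reproduced.

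**2. Range of the baseline score.**
- Open skin in at least one graded zone: minimum 1 × 30 = 30. Partial loss carries the same weight as complete loss, so erosion alone also reaches 30.
- No open skin in any graded zone: 0 if all six look normal, otherwise 1 to 6 × 4 = 24.
- Maximum: 6 × 120 = 720.

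**3. Percent change = 100 × (last − baseline)/baseline.**
- Baseline 0: undefined.
- Baseline 3 (redness over 1-25% of three zones), one zone gaining 1-25% epidermal loss with redness unchanged: (33 − 3)/3 = +1000%.
- Baseline 6 with the same erosion: 30/6 = +500%.
- Baseline 30, rising to 60: +100%.

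**4. Effect of one such value on an arm of 51.** Assume the other 50 have mean −40 and SD 70.
- Shift in mean = (x + 40)/51. For x = 1000 it is 1040/51 = 20.4 points, which is 20.4/45 = 45% of the planned difference. For x = 500 it is 540/51 = 10.6 points.
- SD = √{[49 × 70² + (50/51)(x + 40)²]/50}. For x = 1000 it is 161.3; for x = 500 it is 102.6.

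**5. Effect on power.** Simulation: normal data, SD 70, means 0 (control) and −45 (Cavilon), unranked t-test at 0.05, 20,000 runs, 51 per arm, one subject replaced.

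| One value set to | In Cavilon arm | In control arm |
|---|---|---|
| none | 89% | 89% |
| +100% (30 to 60) | 85% | 92% |
| +300% (30 to 120) | 72% | 93% |
| +650% (4 to 30) | 30% | 93% |
| +1400% (2 to 30) | below 1% | 80% |

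In the control arm a +650% value also inflates the average estimated difference from about 45 to about 58 points.

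**6. Undefined baselines.** Dropping 2 subjects per arm leaves 88.9% power at 0.05, and dropping 5 leaves 86.9%. The problem there is unplanned exclusion after randomization rather than lost power.

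**The case against.** **The group is narrow.** Zone 1 includes the scrotal sac or labia majora and the skin within 2 inches of the anus, and zones 4 and 6 include the medial upper thighs. Many subjects with front or groin involvement would still score. To score no epidermal loss, all denudation must lie in the ungraded area. This stands, and the documents give no frequency.

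**The denuded-skin line could be read as tied to the zones.** It sits in the six-zone bullet. Section 10 also asks for assessments needed by the criteria before the envelope is opened, and the Schedule of Events puts skin assessment in the screening column. A careful site might therefore catch the case. But the line names no zone, and the scoring is listed after allocation.

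**The example is constructed.** It needs front-only denudation, slight redness in graded zones, a new erosion at the last visit, summed zones and no ranking. Ranking would limit the influence of one large value, but it is optional and cannot rank an undefined one.

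**A stronger reading that does not hold.** A reader might infer that Category 2 IAD without any denudation is also eligible. Section 10 says "Only subjects with a Category 2 level of IAD will be enrolled into this study", its Table 1 lists "vesicles/bullae/skin erosion +/- denudation of skin +/- skin infection" as optional signs, and Section 8 describes a population "where the epidermis has been breached, or the skin is denuded". The documents do not support this as a second route:
- Inclusion 3 and the denuded-skin line in Section 10 both require denudation.
- Section 6.3 gives subjects "without denudement at baseline or leaving the study prior to the first assessment day" as its examples of ineligible enrolment.
- Section 8 defers to 8.1 and 8.2, and the Category 2 sentence states a necessary condition only.
- A breached epidermis in a graded zone scores at least 30 in any case.

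The looser wording is an inconsistency to reconcile. Nor does Section 6.3 remove the front-only subject, who does have denudement at baseline.

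**Conclusion.** The point holds in a limited form. Nothing in the eligibility text or the screening order guarantees that a randomized subject has open skin in a graded zone, so a baseline of 0 to 24 is possible. The primary percent change is then undefined or potentially extreme. One value of +1000% would move an arm mean by about 20 points and raise its SD from 70 to about 161; +500% would move it by about 11 points and raise the SD to about 103. These sizes rest on summed zones, an unranked analysis and other subjects at mean −40 with SD 70. They show what one subject could do, not what is likely to happen. The sample size calculation itself is sound on its stated inputs. The change is worth making because it is cheap and the primary endpoint depends on it.

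**What to change.** 1. In Section 8.1 and the synopsis, reword inclusion 3 to require epidermal loss rated at least 1 on the 3M Skin Condition Assessment Tool in at least one of the six graded zones, that is, an IAD score of 30 or more. The denudation requirement can stay beside it, because the tool does not separate erosion from denudation.
2. In Section 10, move the six-zone assessment ahead of opening the envelope.
3. Align the population sentence in Section 8 and the Category 2 sentence in Section 10 with the same threshold.
4. In Section 19 or the SAP, state how a subject still randomized with a baseline of 0 is handled in the primary analysis, and confirm that zone scores are summed.

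**Cost.** A few lines of amendment, using a tool that sites already complete at screening. Subjects with front-only denudation would no longer be enrolled; the primary endpoint cannot measure them.

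**What it leaves.** Every subject enrolled under the rule has a denominator of at least 30, and percent change is bounded between −100% and (720 − 30)/30 = +2300%. Skewness remains: 30 to 120 is still +300%.

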8.2 Subject Exclusion Criteria

Subjects are excluded from participation in this study if **any** of the answers to these following questions is yes.

- 1. If female, is the subject pregnant or breast feeding or has she given birth within the 3 weeks preceding the screening visit?
- 2. Does the subject have a known allergy to acrylates or cyanoacrylates?
- 3. Does the subject have a Stage III, IV, unstageable, suspected deep tissue injury pressure ulcer in the area where the skin is affected by incontinence?
- 4. Does the subject have a preexisting skin disease on the areas affected by incontinence that may make skin assessments for this study difficult?
- 5. Does the skin area affected by incontinence require treatment with a concomitant medication or product?
- 6. Does the subject have an active genital herpes infection?
- 7. Has the subject received antifungal powders in the area affected with IAD within 24 hours prior to enrollment?

- 8. Has the subject received cyanoacrylate based skin protectant (such as Marathon) within 72 hours prior to enrollment?
- 9. Is the facility unwilling to discontinue use for this subject of Dimethicone-containing wipes on the area where the skin protectant product will be applied?
- 10. Is the facility unwilling to discontinue use for this subject of Chlorhexidine Gluconate wipes on the area where the skin protectant product will be applied?
- 11. Does the subject have any medical condition that in the opinion of the investigator should exclude him/her from participating in the study?
- 12. Has the subject been enrolled in any investigational study where product was applied to proposed study sites within 30 days of the screening visit?

9. Subject Consent

The Investigator must ensure that written informed consent to participate in the study is obtained before including any individual as a subject in the study, and before conducting any study-related assessments. The Investigator must provide the prospective subject, or the prospective subject's legally authorized representative, with sufficient opportunity to consider whether or not to participate, and minimize the possibility of coercion or undue influence. The process is designed to 1) give the subject all the information that he/she needs, 2) ensure that the subject understands the information and 3) give the subject a chance to consider study participation. The process should permit the subject to ask questions and exchange information freely.

Specifically, the Investigator is to explain to each subject all elements of informed consent as specified in 21 CFR 50.25. This also includes explaining that photographs will be taken and may be used in publications in ways that do not identify the subject. After the explanation, the subject or legally authorized representative will voluntarily sign and date the consent/assent form if they wish to participate in the study. A copy of the consent/assent form must be provided to the subject or the subject's legally authorize representative. A signed and dated copy of the consent/assent form must be maintained in the Investigator Site File at all times. The informed consent process must be followed, and the subject's participation in the study, must be documented in the subject's medical record/chart.

